## 6.6.2 Impact on Safety Endpoints

No modifications will be made for the analysis of safety data due to COVID-19-related issues. There will not be any additional safety data handling considerations for missing data or treatment interruptions due to COVID-19.

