## 2.0 Study Description

### 2.1 Study Design

This is a 52-week, multi-center, randomized, double-blind, double-dummy, placebo- and active comparator-controlled study to evaluate the safety and efficacy of BMS-986165 vs placebo and apremilast. A total of 600 qualified subjects with moderate-to-severe plaque psoriasis will be enrolled.

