## 2.3 Treatment Assignment and Randomization

At Week 0 (Day 1), subjects who have met all criteria for enrollment will be centrally randomized by a computer-generated randomization schedule in a 2:1:1 ratio to the following treatments:

- BMS-986165 6 mg QD
- Placebo
- Apremilast 30 mg BID (titrated)

The randomization list was generated by the IRT vendor using a permuted block design within each stratum combination level. Randomization will be stratified by geographic region (U.S., Japan [body weight stratum will not be applied in Japan], China [body weight stratum will not be applied in China], Rest of World), previous biologic use (for psoriasis, psoriatic arthritis, or other inflammatory disease only; yes/no), and body weight ( $\geq 90$  kg and  $< 90$  kg).

A treatment group will be assigned by IRT based on the above-described randomization schedule and each subject will be assigned a unique randomization number. In addition, a kit (container) number will be assigned to the subject by the IRT each time study treatment is dispensed. Dummy tablets (placebo to the BMS-986165 6 mg tablet and placebo to apremilast) will be administered to the subjects to maintain blinding. Apremilast will not be used as a treatment arm in China.

At Week 16, subjects receiving placebo will be switched in a blinded manner to BMS-986165 6 mg QD.

At Week 24, subjects originally randomized to apremilast who do not achieve a PASI 50 response will be switched in a blinded manner to BMS-986165 6 mg QD. Subjects originally randomized to apremilast who achieve PASI 50 response at Week 24 will continue to receive apremilast in a blinded manner. The investigative site and other study personnel will not have knowledge of the PASI 50 score at this visit and will therefore remain blinded.

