## 4.2 Safety

The safety outcomes include the following:

- Adverse events (AEs)
  - Treatment-emergent adverse events (TEAEs) – defined as:
    - AEs which occur after the first dose of study treatment through 30 days after the final dose of the study treatment or subject's participation in the study if the last scheduled visit occurs at a later time.
  - Treatment-emergent adverse events of interest (AEIs) for the following events:
    - Skin-related AEs
    - Infection AEs, including influenza
    - Creatine kinase (CK) elevation (evaluated as lab toxicity grade 2 or higher)
    - Malignancy
  - SAEs
  - Deaths
- Clinical laboratory parameters
  - Absolute and change from baseline values
  - Laboratory abnormalities (as determined by Controlled Terminology Criteria for Adverse Events [CTCAE v5.0] grading) presented as the worst postbaseline toxicity group
  - Shifts from baseline to maximum postbaseline value
  - Potential drug induced liver injury (DILI) is defined as a subject who meets the following criteria:
    - 1) ALT or AST elevation >3 times ULN  
AND  
▪ 2) Total bilirubin >2 times ULN, without initial findings of cholestasis (elevated serum alkaline phosphatase)  
AND  
▪ 3) No other immediately apparent possible causes of liver function test elevation and hyperbilirubinemia, including, but not limited to, viral hepatitis, preexisting chronic or acute liver disease, or the administration of other drug(s) known to be hepatotoxic.
    - ALT or AST elevation >5 times ULN
- Vital signs
  - Absolute and change from baseline values
  - Marked abnormalities defined by the below categories:
    - Heart rate:
      - Value > 100 and change from baseline > 30
      - Value < 55 and change from baseline < -15
    - Systolic blood pressure:
      - Value > 140 and change from baseline > 20

Sponsor: Bristol-Myers Squibb

Protocol no: IM011046

- Value < 90 and change from baseline < -20
- Diastolic blood pressure:
  - Value > 90 and change from baseline > 10
  - Value < 55 and change from baseline < -10
- Electrocardiograms (ECGs)
  - Absolute and change from baseline values
  - Marked abnormalities defined by the below categories:
    - QT interval corrected using Fridericia's formula (QTcF):
      - 450 -< 480 msec
      - 480 -< 500 msec
      - $\geq$  500 msec
      - $30 < \text{change from baseline} \leq 60$  msec
      - Change from baseline > 60 msec
      - Males: < 450 msec,  $\geq$  450 msec
      - Females: < 470 msec,  $\geq$  470 msec

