### 6.2.1 Adverse Events

Adverse events will be presented for the number and percentage of subjects and the number of events. Treatment-emergent will be provided in listings. Summary tables will be reported in decreasing frequency based on the BMS-986165 column. Counting for frequency analysis will be by subject and not by AEs, and subjects are only counted once for recurring AEs within each system organ class (SOC) or preferred term (PT); however, the number of total AEs per subject, including multiple occurrences of individual AEs, will also be presented. For summaries of severity, AEs will be reported only at their maximum severity in each subject. Subjects with multiple AEs within a particular SOC or PT will be counted under the category of their most severe event within that SOC or PT.

AE (including deaths) dates will be imputed according to algorithms detailed in [Section 8.0](#). The imputed date of AE onset will be used to assess whether AEs should be considered as treatment-emergent and included in the safety summaries. The original, partial dates will be included in data listings. No imputation will be performed on missing AE seriousness, severity, or relationship; they will be reported as missing.

AEs will be included in a period if the start date of the AE is after the first dispensation date within a period.

An overall summary for the following categories will be presented:

- Deaths
- SAEs
- Related SAEs

Sponsor: Bristol-Myers Squibb

Protocol no: IM011046

- AEs
- Related AEs
- Discontinued treatment due to AEs

The following summaries will also be provided for the following:

- TEAEs by SOC and PT
- Treatment-related TEAEs by SOC and PT
- TEAEs by PT reported in  $\geq 5\%$  of subjects
- TEAEs by PT reported in  $\geq 1\%$  of subjects
- Treatment-related TEAEs by PT reported in  $\geq 5\%$  of subjects
- TEAEs categorized by severity by SOC and PT
- Exposure-adjusted incidence rate (EAIR) for TEAEs by SOC and PT – EAIR is defined in [Section 8.1](#) of the SAP

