## 6.6 Statistical Impacts Due to COVID-19

### 6.6.1 Impact on Efficacy Endpoints

There are no COVID-19-related impacts to the Week 16 and Week 24 endpoints as all subjects remaining in the trial completed these visits prior to COVID-19 restrictions. Key secondary efficacy endpoints involving later visits may be impacted by COVID-19 in the form of missing data and/or a treatment assignment defaulting to BMS-986165. If a subject has missing data or is switched to BMS-986165 from a different treatment due to COVID-19 during the Week 24 through Week 52 period, the subject will be excluded from the analysis.

Key secondary efficacy endpoints that may be impacted include the following:

- sPGA 0/1 response at Week 52 and at Week 24
- PASI 75 response at Week 52 and at Week 24
- PASI 90 response at Week 52 and at Week 24

A sensitivity analysis will also be performed for the above endpoints using the last observed value. The data handling rules to be used are as follows for subjects with missing data or for those subjects who switch to BMS-986165 from a different treatment due to COVID-19:

- If the subject is missing the Week 52 response value (ie, sPGA 0/1, PASI 75, PASI 90), then the last observed response value during the Week 24 through Week 52 period will be carried forward to the Week 52 value
- If the subject is switched to BMS-986165 from a different treatment due to COVID-19, then the last observed response value prior to the switch will be carried forward to the Week 52 value

Censoring rules will be applied to the time to first loss endpoints evaluated for the maintenance of efficacy of BMS-986165 through Week 52 in subjects who were originally randomized to BMS-986165 and impacted by COVID-19-related issues post Week 24:

- Subject has missing visits (ie, efficacy assessments not performed) after Week 24 and assuming loss of response was not observed prior to missing visits:

Sponsor: Bristol-Myers Squibb  
Protocol no: IM011046

- If the subject returns at a later visit and is found to have had a loss of response, midpoint imputation will be used to determine time to first loss (ie, midpoint of the censoring interval).
- If the subject returns at a later visit and has not had a loss of response, then the subject will continue to be evaluated for time to first loss.
- If the subject is discontinued from the study treatment, then the subject will be censored at the time of study treatment discontinuation.

Time to first loss endpoints include:

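### SAP 6.6.2 plans no COVID-19 split for safety, so infection totals and rates for all-exposed or 52-week BMS-986165 are confounded with calendar time when set beside placebo or pooled apremilast

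*SAP*

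**What the plan says.** SAP 6.6 deals with COVID-19. For efficacy, 6.6.1 gives exclusion, carry-forward and censoring rules for endpoints after Week 24. It says nothing is needed at Weeks 16 and 24 because "all subjects remaining in the trial completed these visits prior to COVID-19 restrictions". It also notes that the pandemic could cause "a treatment assignment defaulting to BMS-986165".

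For safety, 6.6.2 says "No modifications will be made for the analysis of safety data due to COVID-19-related issues" and "There will not be any additional safety data handling considerations for missing data or treatment interruptions due to COVID-19". The SAP text available defines no COVID-19 category, exclusion or sensitivity analysis for safety.

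SAP 4.2 lists "Infection AEs, including influenza" among the adverse events of interest. SAP 6.2.1 plans "Exposure-adjusted incidence rate (EAIR) for TEAEs by SOC and PT", and SAP 6.0 uses EAIRs for the summaries of everyone exposed to BMS-986165. Under SAP 8.1 an EAIR assigns the event and the time at risk to the treatment being taken, and time stops at the first onset. Placebo subjects move to BMS-986165 at Week 16, and apremilast subjects without a PASI 50 response move at Week 24 (SAP 2.1).

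**The concern.** Placebo dosing ends eight weeks before the earliest point at which, by 6.6.1, restrictions could have applied to a subject still in the trial. From Week 24 on, everyone on treatment takes BMS-986165 except the apremilast PASI 50 responders. COVID-19 cases therefore collect on BMS-986165 because of when its exposure was accrued, whatever the drugs do.

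With no separate handling, those cases enter the infection, system organ class, serious-event and EAIR totals for all-exposed or 52-week BMS-986165. Beside a placebo rate from Weeks 0-16, or a pooled apremilast rate weighted towards earlier weeks, the BMS-986165 total can look worse from calendar time alone. Infection is a prespecified interest for this drug. A split first made after the data are seen would carry less weight than one planned in advance.

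**Working it through.** The plan gives no figure on this point, so there is none to reproduce. The check is person-time arithmetic.

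**Inputs from the documents**
- Sample size: "A total of 600 qualified subjects with moderate-to-severe plaque psoriasis will be enrolled" (SAP 2.1).
- Allocation: "centrally randomized by a computer-generated randomization schedule in a 2:1:1 ratio" (SAP 2.3), hence 300 BMS-986165, 150 placebo and 150 apremilast.
- Placebo runs 16 weeks. Weeks 24 to 52 are 28 weeks (SAP 2.1, 8.4).

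**Assumptions**
- A fraction *s* of apremilast subjects switches at Week 24. The documents do not give it. The range is 0% to 50%, and 0% is least favourable to the concern.
- There is no dropout, and the COVID-19 hazard is equal on all treatments.
- The 30-day tail in the EAIR definition is ignored.

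**Formulas, in person-weeks**
- BMS-986165 total: 300×52 + 150×36 + 150*s*×28 = 21,000 + 4,200*s*. After Week 24: (450 + 150*s*)×28 = 12,600 + 4,200*s*.
- Apremilast total: 150×24 + 150(1−*s*)×28 = 3,600 + 4,200(1−*s*). After Week 24: 4,200(1−*s*).
- Placebo total: 150×16 = 2,400, about 46 person-years at 52.18 weeks per year. After Week 24: 0.
- BMS-986165 share of all time after Week 24: (450 + 150*s*)/600.

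| *s* | BMS-986165 share of time after Week 24 | Part of BMS-986165 exposure after Week 24 | Part of apremilast exposure after Week 24 | Ratio of the two parts |
|---|---|---|---|---|
| 0% | 75.0% | 12,600/21,000 = 60.0% | 4,200/7,800 = 53.8% | 1.11 |
| 30% | 82.5% | 13,860/22,260 = 62.3% | 2,940/6,540 = 45.0% | 1.39 |
| 50% | 87.5% | 14,700/23,100 = 63.6% | 2,100/5,700 = 36.8% | 1.73 |

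With an equal hazard, the rise in an EAIR is approximately the COVID-19 rate times the part of exposure after Week 24. The last column is therefore the rise on BMS-986165 relative to apremilast. It does not depend on the COVID-19 rate, nor on how much of the time after Week 24 fell in the pandemic, provided that overlap is the same for all treatments.

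**Absolute size (assumed rates)**
- At 5 cases per 100 person-years throughout Weeks 24-52, as *s* goes from 0% to 50%, the EAIR rises by 3.0 to 3.2 per 100 person-years on BMS-986165 (12 to 14 cases). On apremilast it rises by 2.7 falling to 1.8 (4 falling to 2 cases), and on placebo by 0.
- At 2 to 10 per 100 person-years over only 25% to 75% of that time, the rise on BMS-986165 runs from 2×0.25×0.600 = 0.3 to 10×0.75×0.636 = 4.8, about 1 to 21 cases. On apremilast it runs from 2×0.25×0.368 = 0.2 to 10×0.75×0.538 = 4.0.

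**Comparisons that stay clean**
- On the premise of 6.6.1, the Week 0-16 and Week 0-24 summaries precede the restrictions.
- The continuous-treatment groups each have 28/52 = 53.8% of their time after Week 24, so an equal hazard adds equally to both.

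**Why preferred-term rows do not supply the split**
SAP 6.2.1 counts a subject once within a system organ class, and SAP 8.1 stops exposure at the first event. A subject with COVID-19 and later another infection is one event in the class. Without COVID-19 that subject is still one event, but with longer exposure. Subtracting the COVID-19 row from the class total gives neither the right count nor the right denominator.

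**The case against.** Much of the opposing case stands.

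- **Concurrent comparisons.** The planned like-for-like summaries are not materially distorted, and SAP 6.2 presents safety by period and treatment group. A reader might infer that COVID-19 loads BMS-986165 in every comparison. The treatment groups in SAP 6.0 do not support that. The problem is confined to all-exposed or 52-week rates set beside placebo or pooled apremilast.
- **Placebo.** A reader might infer that no COVID-19 case can fall on placebo. Section 6.6.1 dates restrictions, not infections. SAP 4.2 also lets the treatment-emergent window run to the end of participation, and Protocol 7.1.2 keeps subjects who stop treatment in follow-up. If 5% to 20% of the 150 placebo subjects stopped early and stayed (7.5 to 30 of 600), they would hold 1.25% to 5% of subject-time after Week 24. The EAIR is tighter because it needs an event on treatment, with at most a 30-day tail. Essentially none is accurate; none at all is not.
- **Counts and rates.** Most cases fall on BMS-986165 because most person-time does, and an EAIR divides by person-time. Per person-year apremilast is loaded too, only less.
- **Visibility.** COVID-19 would appear under its own preferred term, and adjudicated events are summarised separately (SAP 6.2.1.1). That shows the cases but does not give a total without them.
- **Choice of basis.** Counting all infections is a defensible conservative choice, and safety is descriptive. Comparing treatments only on totals without COVID-19 could hide a real drug effect on viral infection.
- **Unseen material.** The SAP change log refers to a data presentation plan that is not among the documents, and 6.6.2 does not forbid supplementary tables.

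**Conclusion.** The concern holds within limits. SAP 6.6.2 leaves a calendar-time imbalance unaddressed in the non-concurrent infection totals and EAIRs. After Week 24 BMS-986165 holds 75% to 87.5% of subject-time and placebo essentially none. With an equal hazard the all-exposed BMS-986165 EAIR rises 1.1 to 1.7 times as much as the pooled apremilast EAIR.

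The direction rests on the design and on 6.6.1, and holds even if nobody switches. The absence of any apremilast arm in China, and any COVID-19 default to BMS-986165, can only move the share further the same way. The ratio assumes no dropout, an equal hazard and 0% to 50% switching. The absolute size rests wholly on assumed COVID-19 rates and may be negligible at the low end.

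No primary or key secondary efficacy result is touched. This is a minor but nearly free improvement in safety reporting.

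**What to change.** Amend SAP 6.6.2 to keep all planned totals and add supplementary rows that exclude COVID-19 terms for:
- infection adverse events of interest;
- the infections system organ class;
- serious adverse events;
- the corresponding EAIRs, with time at risk recalculated to the first event that is not COVID-19.

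List the preferred terms that count as COVID-19. Show both versions side by side and name neither as the sole basis for comparing treatments.

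No new data are needed. The cost is a short wording change, a second run of a few rows and slightly longer safety tables.

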# 7.0 Sequence of Planned Analyses

## 7.1 Interim Analyses

No interim analysis is planned for this study.

## 7.2 Final Analyses and Reporting

All final, planned analyses identified in this statistical analysis plan will be performed only after the last subject has completed the study and the database has been locked. The randomization codes for all subjects will not be unblinded until after the database has been locked.

Analyses of the palmoplantar pp-PGA 0/1 endpoint are provided for descriptive purposes within the individual CSR due to small sample sizes. A pooled analysis of data from IM011046 and IM011047 will be conducted for the submission.

# 8.0 Conventions

## 8.1 General Definitions

The following data definitions and handling conventions will be used for general analysis:

Term	Definition
Study Day	Study day is calculated as: assessment date – date of first dose + 1
Baseline	Unless otherwise stated, Baseline is defined as the measurement at the randomization visit (Week 0). If the measurement at the randomization visit is missing, then a prior measurement during the screening period may be used as baseline. Baseline assessments must be performed per protocol and standard of care assessments may not be used for baseline. Baseline for each PSSD question will be calculated as the average value over the 7 days prior to the randomization visit. In the event of missing values in the 7 days prior to the randomization visit, daily

Sponsor: Bristol-Myers Squibb  
Protocol no: IM011046

	scores from at least 4 days out of the 7 days can be used to calculate the average score. If > 3 daily scores in the last 7 days are missing for a particular question, then the baseline value for that question will be missing. If any questions are missing baseline after using the described rule, then the baseline value for the subscore using that question and the baseline value for the total score will be missing.
Change from Baseline	Change from baseline is defined as (value at post-baseline visit – value at baseline).
Change in the maximum post-baseline value or change in the worst post-baseline value	Change from baseline in the maximum post-baseline value is defined as highest observed value or grade post-baseline. The change is calculated using this value as the post-baseline value.  Change from baseline in the worst post-baseline value is defined as worst observed value post-baseline. The change is calculated using this value as the post-baseline value.
Concomitant and Prior Medication	Prior medications are defined as medications with a stop date prior to the first dose of study treatment. Concomitant medications are defined as any medications ongoing at the start of study treatment or with a start date on or after the first dose date.
End of Study (EOS) Date	The EOS date is the date recorded on the eCRF that a randomized subject either discontinued or completed the study. If the subject is lost to follow-up, the EOS date will be the date of the last visit assessment obtained.
Exposure-adjusted incidence rate (EAIR)	EAIR = $100 * 365.25 * (\text{total number of subjects with the AE}) / \text{total exposure time for the selected AE under each treatment}$ that a subject is exposed. Where total exposure time for each AE within a treatment is calculated as follows: 
 
• If a subject has at least 1 event while on a particular treatment, then the exposure time for that subject and AE on that treatment is: 
 
◦ First AE onset date – treatment start date (of that particular treatment) + 1
 
 
 
• If a subject does not have an event, exposure time for that AE is: 
 
◦ Treatment stop date (of that particular treatment) – Treatment start date (of that particular treatment) + 1 + 30 days (if subject discontinued or subject completed Period 3 and is not rolling into IM011075 study)
 
◦ Treatment stop date (of that particular treatment) – Treatment start date (of that particular treatment) + 1 (if subject completed Period 3 and is rolling into IM011075 study)
 
 
 
• Total exposure time = sum of exposure time for each AE within a treatment
 

First Dose Date – Study	The date a subject received their first dose on Day 1 as recorded in the eCRF Week 0 [redacted] dosing date or the earliest drug dispensation date.

Sponsor: Bristol-Myers Squibb  
Protocol no: IM011046

Last Dose Date – Study	The date of last recorded dose on the eCRF for a randomized subject.
First Dose Date – Period	The date a subject received their first dose as recorded in the eCRF Week 0 █ dosing date or the earliest drug dispensation date for Treatment Period 1 and the earliest drug dispensation date for Treatment Periods 2 and 3.
Last Dose Date – Period	The date of the last visit in the periods – 1. If a subject prematurely discontinues study treatment within a period, the date of last recorded dose on the eCRF will be used as the last dose date for the period.
Percent Change from Baseline	
Percent change from baseline is defined as ([value at post-baseline visit – value at baseline]/value at baseline) x 100.
 
If the baseline value is 0 and the post-baseline value is also 0, then the percent change from baseline is set to 0.
 
If the baseline value is 0 and the post-baseline is >0, then the percent change from baseline value will be missing.

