Treatments include topical preparations, eg, corticosteroids, vitamin D analogues, calcineurin inhibitors, and salicylic acid; phototherapy modalities, including PUVA (psoralens with UVA) and narrow band UVB; and systemic therapies. In moderate-to-severe disease, systemic treatments are usually needed and may include oral agents (retinoids, methotrexate, cyclosporine, and apremilast) or injectables (eg, biologics such as tumor necrosis factor (TNF) inhibitors etanercept, infliximab, and adalimumab) anti-IL-12/23p40 antibody (ustekinumab), IL-17 antagonists (secukinumab, ixekizumab, and brodalumab), and anti-IL-23p19 antibody (guselkumab). Many of these treatments are associated with increased risk of adverse events (AEs) such as hepatotoxicity and neutropenia (methotrexate); nephrotoxicity (cyclosporine); depression and weight loss (apremilast); serious infections (cytokine inhibitors); candidiasis and Crohn's disease (IL-17 antagonists).

Although effective therapeutic options are available, under-treatment or nontreatment of psoriasis has been reported in up to half of surveyed patients (based on absence of treatment and/or dissatisfaction with treatment). Many patients with severe disease are still being managed with only topicals, and many patients consider their psoriasis treatment to be inadequate. Accordingly, there remains a need for more effective oral options, when compared with currently available agents, that would improve efficacy responses and increase adherence to treatment.

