### **9.5 Safety Analyses**

Safety data will be analyzed for AEs, SAEs, laboratory analytes, vital signs, ECGs, and suicidality and depression. Safety will be summarized using the As-treated population. Categorical data will be summarized as frequency counts and percentages. Continuous data will be summarized using n, mean, standard deviation, median, minimum, and maximum unless otherwise specified.

During the first 16 weeks of treatment, data will be presented for the following treatments:

- BMS-986165 6 mg QD
- Apremilast 30 mg BID
- Placebo

After Week 16, data will be presented for the following treatments:

- BMS-986165 6 mg QD
- Apremilast 30 mg BID
- Placebo to BMS-986165 6 mg QD (starting from Week 16 through Week 52)
- All BMS-986165 6 mg QD (all subjects exposed to BMS-986165 6 mg QD; includes subjects on placebo that switched to BMS-986165 6 mg QD)

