#### Week 16 activities

The coprimary endpoints, static Physician Global Assessment (sPGA) 0/1 and Psoriasis Area and Severity Index (PASI) 75 will be assessed at Week 16. Subjects receiving placebo will be switched in a blinded manner to BMS-986165 6 mg QD at Week 16. Subjects who are randomized to BMS-986165 6 mg QD or apremilast will continue on their assigned treatment regimen in a blinded manner.

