### Week 24 activities

[figure not shown]
At Week 24, subjects originally randomized to apremilast who do not achieve PASI 50 response will be switched in a blinded manner to BMS-986165 6 mg QD. Subjects in the apremilast treatment arm who achieve PASI 50 response at Week 24 will continue to receive apremilast in a blinded manner through Week 52.

During the Week 24 assessment, a subject who has an sPGA  $\geq 3$  or ss-PGA $\geq 3$  may be treated with restricted topicals/shampoos as described in the protocol (Section 6.7.1). These treatments may only be initiated at Week 24, and not at subsequent time points. A subject who is provided these treatments at Week 24 may use them as needed per the investigator's judgement through Week 52.

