## 6.0 Statistical Analyses

Descriptive summaries and analyses will be presented for data captured throughout the study using the following treatment groups.

During the first 16 weeks of treatment, summaries will be provided for the following treatment groups:

- BMS-986165 6 mg QD
- Apremilast
- Placebo

During the first 24 weeks of treatment, summaries will be provided for the following treatment groups:

- BMS-986165 6 mg QD (subjects continuously taking BMS-986165 6 mg QD)
- Apremilast

Summaries will be provided for subjects who have continuous treatment throughout the entire study with either BMS-986165 or apremilast using the following treatment groups:

- BMS-986165 6 mg QD
- Apremilast

Summaries of all subjects exposed to BMS-986165 6 mg QD will also be provided as applicable. Adverse events will be summarized using exposure-adjusted incidence rates (EAIR) for these summaries.

Please note that there will be no Chinese subjects in the apremilast group due to lack of market approval of the agent in China.

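### Safety summaries that include subjects switched to BMS-986165 have only a Week 0 baseline, so their change-based results mix change on placebo or apremilast with change on BMS-986165

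*SAP*

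**What the plan says.** SAP 8.1: "Unless otherwise stated, Baseline is defined as the measurement at the randomization visit (Week 0"; a screening value may stand in if that measurement is missing. The only special case is the PSSD, which is also anchored before randomisation. The same section adds: "Change from baseline is defined as (value at post-baseline visit – value at baseline".

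There are two planned switches. SAP 2.1, Week 16: "Subjects receiving placebo will be switched in a blinded manner to BMS-986165 6 mg QD at Week 16". The second switch comes eight weeks later (SAP 2.1, Week 24) and is described so: "subjects originally randomized to apremilast who do not achieve PASI 50 response will be switched in a blinded manner to BMS-986165 6 mg QD".

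After Week 16, protocol 9.5 presents safety data in four columns. One is for placebo subjects who moved to BMS-986165. Another is for all BMS-986165 exposure, which "includes subjects on placebo that switched to BMS-986165 6 mg QD". SAP 6.0 states: "Summaries of all subjects exposed to BMS-986165 6 mg QD will also be provided as applicable". SAP 5.0 analyses the As-treated population by treatment received, and SAP 6.2 presents safety data by period and treatment group. The list of changes from the protocol in SAP 2.5 does not mention dropping the protocol's post-Week 16 columns.

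The measures that rest on change are:
- by-visit laboratory change (SAP 6.2.3);
- vital signs, including weight (SAP 6.2.4);
- ECG change, including the QTcF change categories (SAP 4.2 and 6.2.5);
- PHQ-8 change and category shifts at every time point (SAP 6.2.6.1).

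The vital-sign marked-abnormality rules combine a level with a change. For high systolic pressure the rule is "Value > 140 and change from baseline > 20". None of these is limited to Week 16.

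**The concern.** For a switched subject, change from Week 0 at a post-switch visit is the sum of what happened before BMS-986165 and what happened on it. Reported under BMS-986165, the first part is credited to a drug the subject was not yet taking. A shift that arose on placebo or apremilast can look like a BMS-986165 effect. A real on-drug rise can be cancelled by an earlier fall.

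The risk is foreseeable here. Protocol section 2 lists among the known risks of existing treatments "depression and weight loss (apremilast", and weight and PHQ-8 are both change-based safety summaries in this trial.

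The SAP also treats its safety outputs unevenly. Adverse-event exposure in SAP 8.1 runs from the start of the particular treatment, and SAP 6.2.1 assigns events to a period by dispensation date. Change-based measures have no matching anchor, so tables for the same BMS-986165 column would follow different attribution rules.

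**Working it through.** The documents give no figure that depends on this rule, so there is nothing to reproduce. The check has four steps.

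**1. Which displays contain switched subjects.** SAP 6.0 describes four. The Week 0-16 display precedes every switch. The Week 0-24 display holds continuous BMS-986165 subjects and apremilast, and ends at the apremilast switch. The whole-study display is limited to continuous treatment. Only the all-exposed summary includes switched subjects. In protocol 9.5, the placebo-to-BMS-986165 and all-BMS-986165 columns include them.

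**2. How many.** Inputs: 600 subjects at 2:1:1 (protocol 4.2), nominally 300 / 150 / 150. Dropout and apremilast switch rates are assumptions. Share = switched / (300 + switched).

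| Assumption | From placebo | From apremilast | All exposed | Switched share |
|---|---|---|---|---|
| No dropout, 20% of apremilast switch | 150 | 30 | 480 | 180/480 = 37.5% |
| No dropout, 40% switch | 150 | 60 | 510 | 210/510 = 41.2% |
| No dropout, 60% switch | 150 | 90 | 540 | 240/540 = 44.4% |
| 10% placebo dropout, 30% switch | 135 | 45 | 480 | 180/480 = 37.5% |
| 10% placebo dropout, 50% switch | 135 | 75 | 510 | 210/510 = 41.2% |
| Placebo switchers only, no dropout | 150 | 0 | 450 | 150/450 = 33.3% |

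The last row follows the safety definition in protocol 9.5, which names only placebo switchers. Protocol 9.4 and SAP 6.0 also cover apremilast switchers.

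**3. Effect on means.** Change from Week 0 = (pre-switch value − Week 0) + (on-drug value − pre-switch value). Within a switch group the first term enters in full. In the pooled mean it is weighted by that group's share. For an assumed mean change of −2 units on apremilast:
- 20% switching: 30/480 × (−2) = −0.13
- 40% switching: 60/510 × (−2) = −0.24
- 60% switching: 90/540 × (−2) = −0.33

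**4. Effect on flags (systolic rule, above 140 and change above 20).**
- Week 0 = 122, Week 16 on placebo = 145, later on BMS-986165 = 145. From Week 0: +23, flagged. From Week 16: 0, not flagged.
- Week 0 = 138, Week 16 on placebo = 122, later on BMS-986165 = 145. From Week 0: +7, not flagged. From Week 16: +23, flagged.

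An illustrative simulation used assumed values: true mean 128, between-subject SD 12, and independent visit-to-visit SD of 8, 10 or 12. Percent flagged:

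| Drift before switch / true BMS-986165 effect (mm Hg) | Week 0 baseline (SD 8 / 10 / 12) | Pre-switch baseline (SD 8 / 10 / 12) |
|---|---|---|
| 0 / 0 | 1.95 / 4.19 / 6.64 | 1.96 / 4.21 / 6.64 |
| +5 / 0 | 5.48 / 8.83 / 11.91 | 2.49 / 5.26 / 8.13 |
| −5 / +5 | 1.96 / 4.20 / 6.66 | 4.12 / 6.84 / 9.49 |

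Without drift before the switch the two baselines agree. With drift, the Week 0 version over-flags in the second row. In the third row it gives essentially the rates seen with no effect at all.

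**Are pre-switch values available?** In protocol Tables 2 and 3, vital signs, weight, ECG, hematology, chemistry, lipids and glucose are scheduled at both Week 16 and Week 24. Visit-day doses follow the blood draws, so visit-day blood samples precede the switch. PHQ-8, HbA1c, urinalysis, lymphocyte subsets and immunoglobulins are scheduled at Week 16 but not at Week 24.

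**The case against.** The best case for leaving the plan alone has five parts.

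- **The exposure is narrow.** Three of the four SAP 6.0 displays contain nobody switched to BMS-986165. The all-exposed summary is planned only where applicable, and the one method stated for it is exposure-adjusted adverse-event rates, which already start at the particular treatment. This stands as a limit. However, protocol 9.5 covers laboratory values, vital signs, ECGs and depression in its post-Week 16 columns, and nothing visible restricts the SAP summary to adverse events.
- **Absolute values are shown beside change.** This also stands: by-visit absolute values and the QTcF level categories do not use baseline. It does not correct the change-based counts.
- **A later baseline has its own fault.** Weight regained after stopping apremilast would count as gain on BMS-986165. For PHQ-8, apremilast switchers would fall back to Week 16, leaving eight weeks of apremilast in the change. This is why the second version should be added rather than replace Week 0.
- **The size is assumed.** The switch rates, the blood-pressure cases and the simulation inputs are not from the documents. The 38-44% counts subjects with an earlier baseline; it does not measure bias.
- **A rule may exist elsewhere.** The SAP's document history refers to a data presentation plan that is not available here, and parts of the public SAP are blacked out. The safety section appears complete and shows no such rule.

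A reader might infer that the whole long-term safety profile is misattributed. The documents do not support that. Adverse events are anchored by period or treatment, and the CTCAE worst-grade and shift tables (SAP 6.2.3) and the eC-SSRS shift and worst-value tables (SAP 6.2.6.2) stop at Week 16.

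**Conclusion.** The point holds for change-based safety measures in columns that include switched subjects, and no further. There, the rule as written gives a BMS-986165 result that contains change from before BMS-986165. Within a switch group the pre-switch change enters in full. In a pooled mean the effect is diluted, to −0.13 to −0.33 units for an assumed −2 on apremilast. Flag counts can be wrong in either direction. The 38-44% share assumes 20-60% of apremilast subjects switch, with up to 10% placebo dropout.

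A reader might also infer that Week 0 is the wrong baseline for the trial. It is right for efficacy, for Period 1 and for subjects randomised to BMS-986165. No randomised comparison or Type I error is touched. These are descriptive tables, but they should be put right before database lock.

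**What to change.** In SAP 8.1 add a rule for the placebo-to-BMS-986165, all-BMS-986165 and all-exposed safety columns only. In switched subjects, change from baseline and change-based marked abnormalities are also derived from the last non-missing value on or before the first BMS-986165 dose (the Week 16 or Week 24 visit). Present this beside the Week 0 version, and show the placebo and apremilast switch groups separately as well as pooled. Tying the rule to the first dose also covers anyone moved to BMS-986165 because of COVID-19 (SAP 6.6.1).

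Keep Week 0 for randomised BMS-986165 subjects, Period 1 and all efficacy endpoints. Reconcile protocol 9.5 with protocol 9.4 and SAP 6.0 on whether apremilast switchers belong in the pooled safety column. If the all-exposed summary is meant for adverse events only, say so.

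The cost is SAP wording, one derived flag and extra table columns, with no new data. State two limits in the SAP. Measures with no Week 24 value (PHQ-8, HbA1c, urinalysis, lymphocyte subsets, immunoglobulins) use Week 16 for apremilast switchers. Change caused by stopping apremilast can appear as change on BMS-986165 under the added baseline.
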